11.6 Record Retention

The investigator will retain study records including source data, copies of case report form, consent forms, HIPAA authorizations, and all study correspondence in a secured facility for at 6 years after the study file is closed with the IRB.

In addition, the Clinical Trials Office (CTO) will keep a master log of all patients participating in the study with sufficient information to allow retrieval of the medical records for that patient.

Please contact the CTO before destroying any study related records.

12 Study Endpoints

12.1 Primary Endpoint

Initial disease response will be assessed 6 weeks after the start of exemestane using the Response Criteria in Solid Tumors (RECIST). Refer to Appendix II.

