This is a phase II study of daily oral exemestane for the treatment of advanced non-small cell lung cancer in post-menopausal women who are progressing on an FDA approved immune checkpoint blockade therapy. The study will be conducted using Simon's two-stage design.³⁰ Stage 1 will enroll 10 patients. If at least 2 objective responses are observed at the first disease re-evaluation at 6 weeks after beginning oral exemestane, Stage 2 will be activated. In Stage 2, an additional 19 patients will be enrolled for a total of 29 patients. If 4 or more objective responses are observed in the 29 patients, exemestane will be deemed worthy of further investigation in this patient population.

4 Patient Selection

Study entry is open to post-menopausal women regardless of race or ethnic background. While there will be every effort to seek out and include minority women, the patient population is expected to be similar to that of advanced non-small cell cancer lung studies at the University Of Minnesota. Men are not eligible for this study as exemestane works by suppressing estrogen production. Women of child-bearing potential are not eligible as exemestane is FDA pregnancy category X – known harm to the unborn.

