Drug Accountability: The study drug supply will be stored and dispensed by the University of Minnesota Medical Center, Fairview Investigational Drug Services (IDS) Pharmacy. IDS will be responsible for drug accountability through the study. IDS will provide study drug to participating MNCCTN sites.

Dosage and Administration Schedule: One 25 mg tablet once daily after a meal

Dose Forms and Strengths: Aromasin Tablets are round, biconvex, and off-white to slightly gray. Each tablet contains 25 mg of exemestane. The tablets are printed on one side with the number "7663" in black.

Storage and Stability: Store at 25°C (77°F); excursions permitted to 15°–30°C (59°–86°F).

Drug Return/Destruction: At the end of the study and after final reconciliation, IDS will destroy any remaining drug according to their current SOP.

Expected Side Effects: refer to Section 6.1.1.

FDA Pregnancy Category X

Contraindications and Counseling:

Patients with a known hypersensitivity to the drug or to any of the excipients

Women of premenopausal endocrine status, including pregnant women

Patients should be informed that they should not take estrogen-containing agents while they are taking exemestane as these could interfere with its pharmacologic action.

Patients should be informed that AROMASIN lowers the level of estrogen in the body. This may lead to reduction in bone mineral density (BMD) over time. The lower the BMD, the greater the risk of osteoporosis and fracture.

Refer to the Aromasin Prescribing Information ([https://www\(pfizer.com/products/product-detail/aromasin](https://www(pfizer.com/products/product-detail/aromasin)) for additional information

8 Measurement of Effect

For the purposes of this study's primary endpoint, patients should be re-evaluated for response every 6 weeks.

Response and progression will be evaluated in this study using the revised Response Evaluation Criteria in Solid Tumors (RECIST) guideline (version 1.1) [*Eur J Ca* 45:228-247, 2009]. Refer to Appendix II for the complete RECIST guidelines.

Quality of life scores, as measured by PROMIS, will be evaluated descriptively at baseline, every 3 weeks during and at the end of treatment visit using medians, ranges, interquartile ranges and boxplots to look for trends in various areas measured by PROMIS.

9 Schedule of Activities

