13.1 Study Design, Objectives and Endpoints

The goal of this phase II study is to estimate the probability of response after treatment of exemestane in post-menopausal women with advanced non-small cell lung cancer progressing while on immune checkpoint blockade. The primary endpoint of treatment response will be assessed at 6 weeks after the start of treatment using RECIST criteria. Secondary endpoints include the proportion of toxicities through 30 days after the last dose or start of new treatment as described in Section 10.2.2, disease-control as measured by response duration, progression-free and overall survival through 12 months from study enrollment and quality of life scores as measured by PROMIS-29 at baseline, every 3 weeks during treatment and at the end of treatment visit. The primary endpoint of response will be evaluated using a two-stage design.

Stage 1 will enroll 10 patients. If 2 or more patients have an objective response after completion of stage 1, an additional 19 patients will be enrolled in stage 2 for a total of 29 patients. If the total number of patients responding is 4 or greater, the treatment will be considered worthy of further investigation.

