13.2 Sample Size

Sample size is based on testing our primary endpoint using Simon's optimal two stage design with a type I error of 5% and power of 80%.³⁰ Our null hypothesis is that the response is $\leq 5\%$ (as all will be progressing on anti-PD1 therapy) and our alternative hypothesis is that response is $\geq 20\%$. If the treatment is truly not effective, there is a 5% chance of concluding that the drug is effective while if the treatment is truly effective, there is a 20% chance of concluding that it is not effective. Up to 10 patients will be enrolled per year.

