Progressive Disease (PD): At least a 20% increase in the sum of the diameters of target lesions, taking as reference the smallest sum on study (this includes the baseline sum if that is the smallest on study). In addition to the relative increase of 20%, the sum must also demonstrate an absolute increase of at least 5 mm. (Note: the appearance of one or more new lesions is also considered progressions).

Stable Disease (SD): Neither sufficient shrinkage to qualify for PR nor sufficient increase to qualify for PD, taking as reference the smallest sum diameters while on study

Evaluation of Non-Target Lesions

Complete Response (CR): Disappearance of all non-target lesions and normalization of tumor marker level. All lymph nodes must be non-pathological in size (<10 mm short axis)

Note: If tumor markers are initially above the upper normal limit, they must normalize for a patient to be considered in complete clinical response.

Non-CR/Non-PD: Persistence of one or more non-target lesion(s) and/or maintenance of tumor marker level above the normal limits

Progressive Disease (PD): Appearance of one or more new lesions and/or *unequivocal progression* of existing non-target lesions. *Unequivocal progression* should not normally trump target lesion status. It must be representative of overall disease status change, not a single lesion increase.

Although a clear progression of "non-target" lesions only is exceptional, the opinion of the treating physician should prevail in such circumstances, and the progression status should be confirmed at a later time by the review panel (or Principal Investigator).

Evaluation of Best Overall Response

The best overall response is the best response recorded from the start of the treatment until disease progression/recurrence (taking as reference for progressive disease the smallest measurements recorded since the treatment started). The patient's best response assignment will depend on the achievement of both measurement and confirmation criteria.

For Patients with Measurable Disease (i.e., Target Disease)

Target Lesions	Non-Target Lesions	New Lesions	Overall Response	Best Overall Response when Confirmation is Required*
CR	CR	No	CR	>4 wks. Confirmation**
CR	Non-CR/Non-PD	No	PR	>4 wks. Confirmation**
CR	Not evaluated	No	PR	
PR	Non-CR/Non-PD/not evaluated	No	PR	
SD	Non-CR/Non-PD/not evaluated	No	SD	documented at least once >4 wks. from baseline**
PD	Any	Yes or No	PD	no prior SD, PR or CR
Any	PD***	Yes or No	PD	

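### The primary endpoint is response at 6 weeks in Sections 12.1 and 13.1, response at every 6-weekly re-evaluation in Section 8, and confirmed best response in Appendix II; one definition is needed before the 4-of-29 decision

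*Combined protocol and SAP*

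**What the plan says.** Two sections place the primary endpoint at a single time. Section 12.1: "Initial disease response will be assessed 6 weeks after the start of exemestane using the Response Criteria in Solid Tumors (RECIST"), with a reference to Appendix II. Section 13.1: "The primary endpoint of treatment response will be assessed at 6 weeks after the start of treatment using RECIST criteria".

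Section 8 attaches a repeated assessment to the same endpoint: "For the purposes of this study's primary endpoint, patients should be re-evaluated for response every 6 weeks". Appendix II has a third version: "The best overall response is the best response recorded from the start of the treatment until disease progression/recurrence". It makes that assignment depend on confirmation as well as measurement. Its table shows confirmation after more than 4 weeks, footnoted as applying to non-randomized trials with response as the primary endpoint. This trial is one.

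The decision rules are timed unevenly. Section 3 ties the Stage 1 gate to one scan: "If at least 2 objective responses are observed at the first disease re-evaluation at 6 weeks". Section 13.1 words the same gate as read once Stage 1 is complete. The final rule, 4 or more responses among 29, has no time point in the Synopsis, Section 3 or 13.1. Section 13.2 sets the null at 5% or less and the alternative at 20% or more, also untimed.

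Under the Synopsis treatment plan, patients with stable disease at week 6 may continue and are scanned every 6 weeks. Section 12.2 lists response duration, progression-free survival and survival, but no best or overall response rate.

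**The concern.** A partial response first seen at week 12 or later can occur and would be recorded. As 12.1 and 13.1 are written, it does not enter the final count or the reported proportion. Under Section 8 and Appendix II it can. With a threshold of 4 in 29, one or two such patients can change the conclusion.

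Two things are at stake. If the wording stays open, the choice between definitions could be made after the responses are known. If the 6-week reading is applied to rates that were meant as any-time rates, the trial has less chance of detecting a 20% response rate than its design supposes.

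**Working it through.** **Inputs**
- Stage 1: 10 patients, continue with 2 or more responses (Synopsis, Sections 3 and 13.1).
- Final: 29 patients, positive with 4 or more responses (same places).
- Null 5%, alternative 20%, type I error 5%, power 80% (Section 13.2).
- Share s of responders who qualify by week 6: not in the documents. Assumed 75%, 60% and 50%.

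**Formula.** For a Stage 1 minimum of g responses and counted response rate p,

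P(positive) = Σ over x = g to 10 of P(X₁ = x) × P(X₂ ≥ 4 − x), with X₁ ~ Bin(10, p) and X₂ ~ Bin(19, p).

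**The plan's own figures first.** At p = 0.20 and g = 2:
- x = 2: 0.3020 × 0.9171 = 0.2770
- x = 3: 0.2013 × 0.9856 = 0.1984
- x ≥ 4: 0.1209
- Sum: 0.596

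At p = 0.05 the result is 0.026. The stated 80% and 5% are therefore not reproduced with the printed Stage 1 minimum. With g = 1 the results are 0.801 and 0.047, which match. That is a separate problem with the Stage 1 rule; both minimums are shown below so that its effect is not charged to the endpoint.

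**Only the 6-week scan counts, any-time rate 20%.** The counted rate is 0.20 × s. For s = 75% it is 0.15, and with g = 2 the sum is 0.2759 × 0.8015 + 0.1298 × 0.9544 + 0.0500 = 0.395.

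| s | Counted rate | P(positive), printed Stage 1 minimum of 2/10 | P(positive), Stage 1 minimum of 1/10 |
|---|---|---|---|
| 100% | 20% | 0.60 | 0.80 |
| 75% | 15% | 0.40 | 0.59 |
| 60% | 12% | 0.26 | 0.41 |
| 50% | 10% | 0.17 | 0.29 |

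**Stage 1 at 6 weeks, final count on any-time response.** Call this the mixed rule. Among the 10 Stage 1 patients, early responders, late responders and non-responders are trinomial with probabilities 0.20s, 0.20(1 − s) and 0.80. The Stage 1 decision uses early responders; the final count uses both kinds.

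| s | Printed Stage 1 minimum of 2/10 | Stage 1 minimum of 1/10 |
|---|---|---|
| 75% | 0.44 | 0.73 |
| 60% | 0.33 | 0.66 |
| 50% | 0.26 | 0.60 |

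**False positives under the mixed rule.** These depend on what 5% means.
- If 5% is an any-time rate, the probability with the printed Stage 1 minimum is at most 0.026, the value when every response is early.
- If 5% is a 6-week rate, the any-time rate is 0.05/s, that is 6.7%, 8.3% or 10%. The probability is then 0.040, 0.052 or 0.062 with the printed Stage 1 minimum, and 0.093, 0.145 or 0.197 with a minimum of 1/10.

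**Confirmation.** A response first seen at the 6-week scan needs a second reading more than 4 weeks later. On the 6-weekly schedule that is the week-12 scan. An endpoint closed at week 6 and a confirmed response cannot both apply.

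**The case against.** The strongest reply is that the text can be read consistently. The first re-evaluation governs only the Stage 1 gate, 12.1 speaks of initial response, and the 4-of-29 rule is untimed, so later responses may already count at the end. That reading is possible. It requires setting aside 13.1, which gives the primary endpoint as response at 6 weeks without limiting this to Stage 1.

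A reader might go further and infer that the plan scores late responders as failures and that its estimate is biased downward. The documents do not support this. No section says how a first response at week 12 is scored. Bias exists only relative to an any-time target, and Section 13.2 does not say that 5% and 20% are any-time rates. If they are 6-week rates, none of the power loss above arises. The 20–30% response rates in the background do not settle the matter: they describe checkpoint blockade itself, whereas 13.2 justifies 5% by the patients already progressing on it. Nor does Appendix II impose 6-weekly scans; that schedule comes from Sections 6.1, 8 and 9.1.

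Three further objections stand. A 6-week endpoint is a legitimate choice for a signal-finding trial. The late-response shares are assumed, and late response is plausible from the proposed immune mechanism but not shown. Counting later responses while the printed gate stays at 6 weeks recovers only part of the loss, for example 0.40 to 0.44.

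**Conclusion.** The point holds as a conflict of definition that bears on the trial's only go/no-go rule. Sections 12.1 and 13.1, Section 8 and Appendix II cannot all define the primary endpoint, and even a sponsor who intends the 6-week reading has to correct Section 8 and settle confirmation.

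Its size is conditional. If 20% is an any-time rate and 75%, 60% or 50% of responders qualify by week 6, counting only the 6-week scan lowers the probability of a positive result from 0.60 to 0.40, 0.26 or 0.17 with the printed gate, and from 0.80 to 0.59, 0.41 or 0.29 with a gate of 1/10. The loss is therefore present whichever gate is used. It does not establish that the plan as a whole excludes late responders, or that it is biased.

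**What to change.** Use one responder definition in Sections 8, 12.1 and 13.1.

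- For the 4-of-29 decision and the reported proportion, count best overall response (CR or PR) at the scheduled 6-weekly scans up to a stated scan, before progression or new therapy. A stated last scan keeps early enrollees from having more chances to respond than late ones.
- State whether the Appendix II confirmation applies.
- Keep the Stage 1 gate at the first re-evaluation for every patient, and word 13.1 to match Section 3.
- State in 13.2 that 5% and 20% refer to this definition. If 5% is really a 6-week rate, the mixed rule can exceed the 5% type I error, as shown above.
- Report the 6-week response rate alongside.

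If the 6-week endpoint is intended, correct Section 8, waive confirmation explicitly, state 5% and 20% as 6-week rates, and add best overall response rate as a secondary endpoint.

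Either route needs only amendment wording, since the scans are already scheduled. Under the first, the final readout waits for later scans of the last patients in stable disease: 6 weeks longer if the last counted scan is week 12 (12 − 6), 12 weeks longer if it is week 18 (18 − 6).

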12.2 Secondary Endpoints

Toxicity will be assessed from the 1st dose of exemestane through 30 days after the last dose, or the start of a new anti-cancer treatment, whichever is earlier. Toxicity severity will be graded using the Common Toxicity Criteria for Adverse Events (CTCAE) version 4. Attribution and expectedness will be assigned per the definitions found in Section 10.1.

Response duration, progression-free survival and survival will be assessed until 1 year after study enrollment based on the definitions found in RECIST 1.1 (Appendix II).

Quality of life will be assessed by use of PROMIS-29 at baseline, every 3 weeks while on study drug and at the end of treatment visit.

13 Statistical Considerations

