Treatment Plan	
Eligible, consenting patients will take exemestane 25 mg once daily by mouth after a meal for a minimum of 6 weeks (2 treatment courses) while continuing on treatment with an FDA-approved anti-PD1 or anti-PD1 antibody. A disease re-evaluation will be performed at 6 weeks and those experiencing a complete response (CR), partial response (PR) or stable disease (SD) based on the Response Evaluation Criteria in Solid Tumors (RECIST) may continue exemestane daily with standard of care ICB until disease progression, unacceptable side effects, or patient refusal/non-compliance. Patients are seen in clinic every 3 weeks with a disease re-evaluation every 6 weeks.
 
An end of treatment visit occurs 4 weeks after the last dose of exemestane or the start of a new therapy, whichever is earlier. All patients are followed for response until disease progression or the start of a new treatment, then for survival through 1 year from study enrollment.

Key Inclusion Criteria	
Advanced stage non-small cell lung cancer (NSCLC) currently receiving an FDA approved anti-PD1 or anti-PDL1 therapy with progressive diseaseSufficient tumor tissue from the diagnostic or subsequent biopsy either as a block or a minimum of 5 slides for estrogen receptor and aromatase analysisFailed at least 1 prior FDA approved treatment regimen for advanced NSCLC - Patients with EGFR/ALK/ROS1 rearrangements should have received an FDA-approved TKI prior to enrollment on this trial.Measureable disease per RECISTPost-menopausal defined as 1 year or more of amenorrhea and if < 55 years of age estradiol assay < 20 pg/mLECOG performance status 0, 1, or 2
Key Exclusion Criteria	
Untreated or unstable CNS diseaseInability or unwillingness to swallow tabletsCurrently using hormone replacement therapy (oral or patch) or/and phytoestrogen supplements (i.e. black cohosh)
Enrollment:	Stage 1: 10 patients, Stage 2 if activated, 19 additional patients

Treatment Schema

* or unacceptable toxicity, patient refusal/noncompliance/> 3 week break from therapy, or, in the opinion of the treating physician stopping therapy is in the best interest of the patient

- Clinic visit every 3 weeks during treatment
- Maintain SOC ICB specific dosing schedule
- Disease reassessment every 6 weeks during exemestane treatment

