1.2 Secondary Objectives

- To determine the toxicity profile of daily exemestane in combination with immune checkpoint blockade therapy in this patient population.
- To estimate the disease control rate, progression-free survival (PFS), and overall survival (OS) of exemestane for up to 1 year from study enrollment in post-menopausal women with previously treated advanced NSCLC.
- To estimate quality of life during study treatment and for one month following discontinuation of study treatment.

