FDA approved agents for the second and third line therapy of NSCLC includes docetaxel, pemetrexed, and erlotinib². These include two chemotherapeutic agents that are currently approved and in use for second line therapy: docetaxel (75 mg/m²) (response rates of 6.7% - 8.8%; Median survival of 5.7 months to 7.9 months and 1 year survivals of about 30%); and pemetrexed (response rate of 9.1%, median survival of 8.3 months and 1 year survival of 29.7%)³⁻⁵. In several randomized controlled trials, immune checkpoint antibodies, have now been approved in the 2nd or 3rd line setting based on improved overall survival compared to docetaxel. Thus, pembrolizumab, nivolumab, and atezolizumab are now commonly used 2nd line agents for the treatment of NSCLC. The major advance of immune checkpoint blockade is that in patients who respond, the duration of response is quite long and some patients (~15%) remain in remission for several years after the initiation of treatment. Unfortunately, the objective response rate remains relatively low in the range of 20-30%. Thus, the majority of patients will not respond to such therapy. While modest improvements have been made in survival and quality of life in patients with advanced NSCLC there is a need to explore new agents with novel mechanisms of action in this patient population. Moreover, novel combination therapies with immune checkpoint blockade are actively sought to improve upon the low response rates with this therapy.

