6.1 Exemestane Dosing Plan

Exemestane is self-administered as a single, 25 mg tablet by mouth following a meal once daily at approximately the same time each day. If the dose is missed by more than 8 hours, the patient will skip that dose and take the next scheduled dose at the usual time.

Exemestane will continue once daily until disease progression, unacceptable side effects, patient refusal/non-compliance, or the treating physician feels discontinuing therapy is in the best interest of the patient.

The patient will be provided with a daily drug log to record the time of administration, side effects, and any missed doses. The patient will be instructed to bring the drug log and study drug bottles (including any empties) to each appointment for reconciliation.

During the first treatment cycle only, the patient will be contacted by a member of the research staff 8 to 12 days after dosing was started to inquire "how things are going" and to see if she has any questions or concerns.

For the purpose of this study each 3 week (21 day) dosing period will be considered a treatment course. A disease re-assessment will be done after every 2 treatment courses.

Participants who do not undergo the 1st disease re-evaluation will be considered unevaluable and replaced.

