6.5 Duration of Study Participation

Direct study participation stops with the end of treatment visit; however all patients are followed for 1 year from the start of study treatment or until death, whichever is shorter.

Patients who discontinue treatment due to disease progression are followed for survival only (medical record review, local MD or patient contact) for 1 year from study treatment start.

Patients who discontinue treatment in the absence of disease progression are followed for disease response per standard of care until disease progression or the start of a new treatment, whichever is shorter and then for survival only for 1 year from study treatment start.

By 1 year from treatment start, all patients should have a last known date alive or a death date with cause recorded in OnCore, as well as, an initial date for disease progression in association with exemestane treatment.

7 Exemestane Drug Information

Names: exemestane, AROMASIN®, 6-Methyleneandrosta-1,4-diene-3,17-dione

Category: Aromatase Inhibitors

Indications: 1) For the treatment of advanced breast cancer in postmenopausal women whose disease has progressed following tamoxifen therapy and 2) adjuvant treatment of postmenopausal women with estrogen-receptor positive early breast cancer who have received two to three years of tamoxifen and are switched to exemestane for completion of a total of five consecutive years of adjuvant hormonal therapy.

Pharmacology: Aromatase is an enzyme that converts hormones to estrogen in the body's adrenal glands. The aromatase inhibitors (AIs) are drugs that reduce estrogen levels by blocking the action of aromatase in the adrenal glands. The selective AIs (SAIs) selectively reduce levels of estrogen without interfering with levels of other

steroid hormones that are produced by the adrenal gland. Drugs in this class include anastrozole (Arimidex™), letrozole (Femara™) and exemestane (Aromasin™)

Availability: For the purposes of this study a commercial formulation of Aromasin will be provided by the manufacturer, Pfizer. The study specific drug reorder form is attached in OnCore under this study. It is recommended that a drug inventory sufficient to treat study subjects for approximately four (4) weeks be maintained while waiting for additional ordered supplies.

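### Response duration and PFS are cut off 1 year after enrollment while treatment and scans continue uncapped, so response duration could be mostly censored if its true median exceeds about 10.6 months

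*Combined protocol and SAP*

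**What the plan says.** **The cut-off.** Section 12.2: "Response duration, progression-free survival and survival will be assessed until 1 year after study enrollment". Section 13.1 repeats it: "disease-control as measured by response duration, progression-free and overall survival through 12 months from study enrollment". The secondary objective in Section 1.2 carries the same horizon: "overall survival (OS) of exemestane for up to 1 year from study enrollment".

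**Treatment and scans.** Section 6.1 sets no time limit: "Exemestane will continue once daily until disease progression, unacceptable side effects, patient refusal/non-compliance". Section 9.1 schedules CT every 6 weeks during exemestane and a DEXA scan every 12 months, so treatment beyond a year is foreseen.

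**Follow-up for response.** In the synopsis (Treatment Plan), patients are "followed for response until disease progression or the start of a new treatment"; the 1-year limit there belongs to survival. Appendix II, which Section 12.2 cites for its definitions, runs duration of response to objectively documented progression and gives no 1-year limit.

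**Section 6.5.** The year starts elsewhere: "all patients are followed for 1 year from the start of study treatment or until death, whichever is shorter". The section adds that by 1 year all patients should have, besides a survival status, "an initial date for disease progression in association with exemestane treatment".

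**Analysis.** Section 13.3 uses Kaplan-Meier for survival and PFS. For disease control, which Section 13.1 measures by response duration among other things, it lists medians, ranges, interquartile ranges and box-plots.

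**The concern.** A patient still responding on exemestane at 1 year goes on being scanned under the protocol, but those scans do not count toward response duration. A positive trial may rest on as few as 4 responders, so each truncated duration removes a noticeable part of the information on durability. The primary endpoint is a single early reading, which makes duration useful supporting information.

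Two wording problems add to this. Section 6.5 expects a date that a patient without progression cannot have, and it counts from a different day than Sections 1.2, 12.2 and 13.1. Section 13.3 does not say how an ongoing response enters a median or box-plot. If the truncated value is entered as if the response had ended, duration is understated and nothing in the results shows it.

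**Working it through.** The plan states no response duration and no censoring figure, so there is nothing of its own to reproduce. The medians below are assumptions.

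**1. Observable window.** Response is first assessed 6 weeks after the start of exemestane (12.1), and duration starts when CR or PR criteria are first met (Appendix II). Ignoring any gap between enrollment and first dose:
- 52 − 6 = 46 weeks; 46/52 × 12 = 10.6 months.
- With the ±7-day scan window: 45 to 47 weeks, or 10.4 to 10.8 months.
- A response first seen at week 12 leaves 40 weeks: 40/52 × 12 = 9.2 months.

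**2. Share censored.** For exponential durations with median m months, S = 2^(−10.6/m). This passes 50% only when m exceeds about 10.6.

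**3. Effect of a common cut-off 1 year after the last enrollment.** At 10 patients per year (13.2), 29 patients take 2.9 years, or 34.8 months. With uniform accrual, the average share censored is S × (1 − 2^(−34.8/m)) / (34.8 × ln 2 / m).

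| Assumed median (months) | Censored, current plan | Censored, common cut-off |
|---|---|---|
| 6 | 29% | 0.293 × 0.982/4.020 = 7% |
| 9 | 44% | 0.441 × 0.931/2.680 = 15% |
| 12 | 54% | 0.541 × 0.866/2.010 = 23% |
| 18 | 66% | 0.664 × 0.738/1.340 = 37% |

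The last column is a best case: it treats every responder as staying on exemestane until progression.

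**4. What this means with few responders.** Success needs at least 4 responses (13.1); at a true 20% rate, 29 × 0.20 = 5.8 are expected. With 4 responders, a Kaplan-Meier median is reached only if at least 2 responses end inside the window. That probability is 1 − S⁴ − 4(1 − S)S³:
- median 6 months (S = 0.293): 92%
- median 12 months (S = 0.541): 62%
- median 24 months (S = 0.736): 29%

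**5. PFS.** The share progression-free at 12 months is 2^(−12/m): 6%, 25% and 35% for assumed medians of 3, 6 and 8 months. As a rough bound, the 1-year survival of about 30% that Section 2.1 gives for second-line docetaxel would leave at most 0.30 × 29 = 8.7, about 9 patients, progression-free at the cut-off. That benchmark comes from a different population.

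**6. Wording.** Under Section 6.1, a patient in response at month 12 is still on drug and has no progression date, so the expectation in Section 6.5 cannot be met for her. Under Section 13.3, an ongoing response entered as 10.6 months makes the plain median at most 10.6 months, however long responses really last.

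**The case against.** The strongest reply is that the horizon is deliberate: the secondary objective itself is limited to 1 year, Sections 12.2 and 13.1 match it, and the version log records an edit made to align them. That stands as far as it goes. The plan is consistent on the cut-off of these endpoints, and a longer window is an improvement rather than the correction of an error. It does not explain why on-treatment scans already scheduled should go unused.

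Several stronger readings are tempting, and the documents do not support them:
- **That duration will be mostly censored.** This needs a median above about 10.6 months, and no duration is given for this population. Section 2.1 does say of checkpoint blockade that "the duration of response is quite long and some patients (~15%) remain in remission for several years", but that describes the class in general. These patients are already progressing on it, Section 13.2 sets the null response rate at 5% for that reason, and Section 2.4 says most responders eventually become resistant.
- **That PFS is seriously damaged.** Most PFS events should fall within a year, and Kaplan-Meier handles the remaining administrative censoring.
- **That the decision on further study is compromised.** It rests on 4 or more responses in 29, with response read at 6 weeks; duration does not enter it.
- **That Section 6.5 makes staff invent progression dates.** Nothing instructs them to. The same section provides for patients who stop without progression, and its sentence can be read as a loose completeness target. It still needs rewording.

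The gain is also modest. At a 12-month median, 54% falling to 23% is about two fewer censored durations among 6 responders (6 × 0.31 = 1.9), and a responder enrolled last still has only about 10.6 months.

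**Conclusion.** The point holds as a low-cost improvement. Response duration cannot be observed beyond about 10.6 months, although treatment and CT continue without a cap. Censoring ranges from 29% to 66% over assumed medians of 6 to 18 months and reaches a majority only above about 10.6 months. These figures assume exponential durations, response first met at the week-6 scan, and no delay between enrollment and first dose; the comparison with a common cut-off also assumes uniform accrual at 10 per year.

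The inconsistencies do not depend on any assumed duration: Section 6.5 expects a progression date for everyone and uses a different time origin, and Section 13.3 leaves the handling of ongoing responses open. All of this concerns descriptive secondary reporting. No error rate or decision rule changes.

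**What to change.** 1. **Sections 12.2 and 13.1, with matching wording in Section 1.2 and the synopsis objective.** For patients still on exemestane at 1 year, use all protocol-scheduled scans up to a common data cut-off, 1 year after the last patient enrolls, for response duration and PFS. Keep 1-year PFS and OS as landmark estimates.
2. **Section 13.3.** Estimate response duration by Kaplan-Meier, or list durations individually with ongoing responses marked as censored.
3. **Section 6.5.** Replace the required progression date with either the progression date or the date of the last disease assessment without progression. Reconcile the time origin with Sections 12.2 and 13.1, and make the 1-year follow-up sentence consistent with item 1.

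The cost is amendment wording and somewhat longer data entry for the few patients treated beyond 1 year. No visits or scans are added, and follow-up of patients off treatment is not extended, so those who stop without progression remain censored as now.
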